## 1 PROTOCOL SUMMARY

### 1.1 SYNOPSIS

Title:	Feasibility Study of Multi-Treatment Posterior Nasal Nerve Modulation for Treatment of Chronic Rhinitis
Study Description:	Prospective, non-randomized, feasibility study of adult patients for treatment to the posterior nasal nerve using cryotherapy at multiple treatment sites within the nasal cavity.
Objectives:	
Evaluate the feasibility of treatment to the posterior nasal nerve at both the middle and inferior meatus locations within the nasal cavity.
 
Primary Objective: Evaluate the safety of treatment to the inferior meatus location
 
Secondary Objectives: Evaluate the effectiveness and tolerability of treatment at the inferior meatus location

Endpoints:	
Primary Endpoint: Incidence of procedure related Serious Adverse Events (SAEs) and/or Serious Adverse Device Effects (SADE)
 
Secondary Endpoints:
 
 
• Incidence of procedure-related Adverse Events (AEs) or Adverse Device Effects (ADEs).
 
• Tolerability of treatment via verbal report of pain/discomfort.
 
• Nasal symptoms using rTNSS scale at 30- and 90-Days post-treatment.
 
• Nasal congestion and turbinate hypertrophy as assessed by physician at 30- and 90-Days post-treatment.
 
 
Exploratory Endpoints:
 
 
• Physician Evaluation of ease of treatment delivery using study device for inferior meatus location.
 

Study Population:	Up to 30 adult subjects diagnosed by ENT Physician with chronic rhinitis will be enrolled and treated in-office.
Clinical Site(s)	Up to 5 U.S. sites
Study Device:	Arrinex ClariFix™ Cryotherapy Device
Study Duration:	9 Months
Participant Duration:	Approximately 3.5 months

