one (1) probable adverse device effect and procedure-related, two (2) procedure related adverse events, and two (2) serious adverse events (one not related, and one possible device related).

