## 9.2 SAMPLE SIZE DETERMINATION

Inasmuch as this is a feasibility study with N=30, no formal power and/or sample size estimations were performed. The proposed sample size is comparable to those in other trials of this nature in this discipline.

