#### 9.4.4 SAFETY ANALYSES

The overall incidence (i.e., number and percent of subjects with 1 or more adverse event) of adverse events, serious adverse device events, serious adverse events, and device and/or procedure related events (e.g., possibly, probably or definitely related) will be calculated from time of treatment through the entire duration of follow-up. The overall incidence of mild, moderate and severe events will be calculated by considering the most severe event for each subject.

In addition, the overall incidence for each adverse event type will be calculated. The adverse event types will be classified as defined in Section 8.4.

---

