3.1.1 Study Endpoints

The primary endpoint is the incidence of procedure-related serious adverse events (SAEs) and/or serious adverse device effects (SADEs)

Secondary endpoints are:

- Incidence of procedure-related adverse events (AEs) and/or adverse device effects (ADEs)
- Tolerability of treatment as rated by participant verbal report of pain/discomfort on the 11-point Numeric Pain Rating Scale (NPRS)
- Change from baseline in nasal symptoms using the reflective Total Nasal Symptom Score (rTNSS) at 30 and 90 days post treatment
- Change from baseline in nasal congestion and turbinate hypertrophy as assessed by nasal endoscopy 30 and 90 days post treatment

Additional exploratory analyses are:

- Procedural characteristics
- Physician evaluation of ease of treatment delivery using study device for inferior meatus location
- Change from baseline in patient-reported outcome (PRO) assessments at 30 and 90 days post treatment:
 - Nasal Obstruction Symptom Evaluation (NOSE)
 - Sino-Nasal Outcomes Test (SNOT-22)
 - Nasal symptom visual analog scale (VAS)
 - Mini Rhinoconjunctivitis Quality of Life Questionnaire (mini RQLQ)

- Physician assessment of participant change from baseline as measured by the Clinical Global Impressions – Improvement

All statistical analyses will be performed using SAS (version 9.4), unless otherwise noted.

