3.1.3 Sample size calculation and assumptions

A convenience sample of 30 treated participants was determined to be adequate for the study.

4 General Analysis Definitions

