8.2.1 Serious adverse events

The primary safety endpoint is the number of participants with 1 or more SAEs and/or SADEs. SADEs are SAEs that are adjudicated to be related (possibly, probably, or definitely) to the ClariFix device and/or procedure. The total number of SAEs will also be presented.

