10.4 Sensitivity and missing data analyses

Due to the small sample size and short-term follow-up, no sensitivity or missing data analyses are planned.

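### The primary safety incidence is planned without a confidence interval, and 30 participants are called adequate without saying that 0/30 still leaves rates up to 11.6% inside the exact 95% interval

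*SAP*

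**What the plan says.** - **Endpoint as analysed.** SAP 8.2.1: "The primary safety endpoint is the number of participants with 1 or more SAEs and/or SADEs". It adds the total number of SAEs.
- **Endpoint as defined.** SAP 3.1.1 and protocol section 3 call it an incidence and restrict it to procedure-related SAEs and/or SADEs.
- **Summary in the protocol.** Section 9.4.4 defines overall incidence as "number and percent of subjects with 1 or more adverse event", applies it to serious and related events, and runs it from treatment to the end of follow-up. No interval is mentioned.
- **Denominator.** All treated participants (SAP 4.3 and 8.1).
- **Sample size.** SAP 3.1.3: "A convenience sample of 30 treated participants was determined to be adequate for the study". Protocol 9.2: "Inasmuch as this is a feasibility study with N=30, no formal power and/or sample size estimations were performed". The protocol synopsis makes 30 a ceiling: "Up to 30 adult subjects diagnosed by ENT Physician with chronic rhinitis will be enrolled and treated in-office".
- **Hypothesis and thresholds.** SAP 3.1.2 states that the primary endpoint has no formal hypothesis. SAP 10.1 sets no termination criteria, and no acceptable rate appears anywhere.
- **Missing data.** SAP 10.4: "no sensitivity or missing data analyses are planned".

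**The concern.** With no hypothesis, no threshold and no comparator, the primary result can only be an estimate, and an estimate needs a statement of precision. The plan gives a test, an alpha level and a fallback method to rTNSS and to the exploratory NOSE, SNOT-22, VAS and mini RQLQ scores. The primary endpoint gets a number and a percent.

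This matters most when no event is seen. The figures 0 and 0% look the same at any sample size, so only the interval shows how much 30 participants can exclude. The prior data do not fill the gap: protocol 2.3 describes the 100-subject study as treating the middle meatus, whereas the inferior meatus is the location whose safety is in question here.

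**Working it through.** **Is there a figure to reproduce?** No. Both documents say that 30 was not derived from a power or sample-size calculation. The check is therefore what 30 delivers.

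**Inputs**

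- n = 30 treated (SAP 3.1.3), a ceiling in the protocol.
- Confidence level: two-sided 95%, matching the two-sided 5% convention in protocol 9.4.1.
- Prior serious events (protocol 2.3): the pilot had 0 device- or procedure-related SAEs in 27 subjects. The 100-subject study had 2 SAEs, of which 1 was possibly device related. That is 1/100 for related events and, if the two were in different subjects, 2/100 for any SAE.
- Prior loss by Day 90 (protocol 2.3): 3/27 in the pilot and 2/100 in the later study.

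**Precision**

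For zero events the exact (Clopper-Pearson) two-sided 95% upper limit is 1 − 0.025^(1/n). The one-sided 95% bound is 1 − 0.05^(1/n).

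| Result | Exact two-sided 95% CI |
|---|---|
| 0/30 | 0% to 11.6% (1 − 0.025^(1/30) = 0.1157) |
| 1/30 | 0.1% to 17.2% |
| 2/30 | 0.8% to 22.1% |
| 0/25 | 0% to 13.7% |
| 0/20 | 0% to 16.8% |

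The one-sided 95% bound for 0/30 is 1 − 0.05^(1/30) = 9.5%.

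**How plausible is zero?**

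P(0 of 30) = (1 − p)^30:

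- p = 1% (prior related rate): 0.99^30 = 0.740
- p = 2% (prior any-SAE rate): 0.98^30 = 0.545
- p = 5%: 0.95^30 = 0.215
- p = 10%: 0.90^30 = 0.042

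Zero is the single most likely count only when P(1) < P(0), that is 30p/(1 − p) < 1, or p < 1/31 = 3.2%. At 5%, P(1) = 30 × 0.05 × 0.95^29 = 0.34, which exceeds P(0).

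**Effect of loss to follow-up**

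A treated participant who leaves before Day 90 with no recorded event stays in the denominator as a non-event. Pooled prior loss is (3 + 2)/(27 + 100) = 5/127 = 3.9%, or about 1 of 30. The pilot rate alone gives 30 × 3/27 = 3.3, or about 3 of 30.

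- 0/29: 1 − 0.025^(1/29) = 11.9%
- 0/27: 1 − 0.025^(1/27) = 12.8%

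The upper limit therefore moves by 0.3 to 1.2 percentage points.

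**Which count?**

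SAP 8.2.1 defines SADEs as related SAEs, so SAEs and/or SADEs amounts to any SAE. SAP 3.1.1 restricts the endpoint to procedure-related events. The choice changes which prior rate applies (1% or 2%) but not the limit for 0/30.

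**The case against.** The strongest reply is that this is openly a feasibility study. The lack of a power calculation is disclosed, adequacy is claimed only for a study of that kind, no estimate is biased, and any reader can compute an exact interval from n and N. All of that stands. Absence of power is not the complaint here, and the point concerns reporting rather than validity. It does not remove the gap, because a study that disclaims hypothesis testing depends on estimation for its primary result.

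Several stronger readings are tempting, and the documents do not support them:

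- *The whole analysis is a bare count.* That describes SAP 8.2.1 only. Protocol 9.4.4 adds a percent and incidence by worst severity, and SAP 8.2.2 adds a listing by participant.
- *A result of 0/30 would be declared safe.* A reader might infer this because the summary in protocol 2.3 describes the two earlier studies as having shown safety, with no interval given. No passage sets such a rule for this trial.
- *Zero is the most likely result even at rates far above prior experience.* This is true only below about 3.2%. At 5%, one event is more likely than none.
- *Losses hide a material risk.* The 3/27 loss comes from the pilot alone. In the 100-subject study 98 completed 90 days. An event recorded before loss still counts, and SAP 4.1 lists early discontinuations with reasons.
- *The interval is the only safety conclusion available.* The plan also yields severity, relatedness, pain by location, and graded local findings.

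**Conclusion.** The point holds as a gap in precision reporting. The primary incidence is planned as a number and percent with no interval in either document, and 30 is called adequate with no stated precision. If all 30 are treated and none has an event, the exact two-sided 95% interval runs from 0% to 11.6%. With fewer treated it is wider, for example to 13.7% at 25.

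The 11.6% assumes the Clopper-Pearson method and a two-sided 95% level. It should not be presented as a one-sided 95% exclusion, for which the figure is 9.5%. The probabilities of seeing zero assume independent participants with a common rate. The prior rates are only a guide, since they come from the earlier studies rather than from treatment at both locations. The change is worth making because it is nearly free and determines what the primary result can be said to exclude.

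**What to change.** 1. **Reconcile the count first.** Make SAP 8.2.1 agree with SAP 3.1.1 and protocol section 3 on whether the primary count is any SAE or only procedure-related SAEs and SADEs. Otherwise the interval may be put around the wrong number.
2. **SAP 8.2.1 and 8.2.2.** Report n/N, percent and the exact (Clopper-Pearson) two-sided 95% confidence interval. Word the safety conclusion by the upper limit.
3. **SAP 3.1.3.** Replace the unqualified claim of adequacy with a precision statement: *if no event is seen in 30 treated participants, the upper limit of the exact two-sided 95% confidence interval is 11.6%; it is wider if fewer are treated.*
4. **Minor supporting figure.** Give the same interval for participants followed to Day 90 or with an event. The effect is expected to be small (11.9% for 0/29, 12.8% for 0/27).

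The cost is SAP wording and about one line of SAS code, with no change to design, enrolment or conduct. The drawback is that the headline safety figure will look less favourable.

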8.2.2 All device-related/procedure-related adverse events

The secondary safety endpoint is the number of participants with 1 or more AE and/or ADE. ADEs are AEs that are adjudicated to be related (possibly, probably, or definitely) to the ClariFix device and/or procedure. The total number of AEs and ADEs will also be presented.

A listing by participant of all SAEs, SADEs, and ADEs will be provided.

9 Protocol Deviations

Protocol deviations will be summarized by deviation type, and overall using counts and percentages. A listing of all protocol deviations by participant will also be provided.

10 Additional Statistical Analyses

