## 8.4 ADVERSE EVENTS, ADVERSE DEVICE EFFECTS, SERIOUS ADVERSE EVENTS AND UNEXPECTED ADVERSE DEVICE EFFECTS

In this study, the following types of adverse events will be collected and documented:

- ClariFix Device-related Adverse Device Effects (ADE)
- Cryotherapy procedure-related Adverse Events (AE)
- Head, ear, nose, throat, and breathing/lung related AEs, including anticipated AEs
- All Serious Adverse Events (SAE)
- Unanticipated Adverse Device Effects (UADE)

Anticipated adverse events are identified in the ClariFix IFU (See Appendix I).

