### 8.4.2 DEFINITION OF ADVERSE DEVICE EFFECT (ADE)

Any adverse event related to the use of the study device. An adverse event is an untoward medical occurrence, unintended disease or injury, or untoward clinical sign in subjects.

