#### 8.4.5.2 RELATIONSHIP TO STUDY INTERVENTION

All adverse events (AEs) must have their relationship to both the study device and study procedure assessed by the clinician who examines and evaluates the subject based on temporal relationship and his/her clinical judgment. The degree of certainty about causality will be graded using the categories below. In a clinical trial, the study product must always be suspect.

- **Definitely Related** – There is clear evidence to suggest a causal relationship to either the study device or the study procedure, and other possible contributing factors can be ruled out. The clinical event, including an abnormal laboratory test result, occurs in a plausible time relationship to study device or the study procedure and cannot be explained by concurrent disease or other drugs or chemicals. The event must be phenomenologically definitive.
- **Probably Related** – There is evidence to suggest a causal relationship to either the study device or the study procedure, and the influence of other factors is unlikely. The clinical event, including an abnormal laboratory test result, occurs within a reasonable time after administration of the study intervention, is unlikely to be attributed to concurrent disease or other drugs or chemicals.
- **Potentially Related** – There is some evidence to suggest a causal relationship to either the study device or the study procedure (e.g., the event occurred within a reasonable time after study procedure). However, other factors may have contributed to the event (e.g., the participant’s clinical condition, other concomitant events).
- **Unlikely to be related** – A clinical event, including an abnormal laboratory test result, whose temporal relationship to either the study device or the study procedure makes a causal relationship improbable (e.g., the event did not occur within a reasonable time after study procedure) and in which other drugs or chemicals or underlying disease provides plausible explanations (e.g., the participant’s clinical condition, other concomitant treatments).
- **Not Related** – The AE is completely independent of either the study device or the study procedure, and/or evidence exists that the event is definitely related to another etiology. There must be an alternative, definitive etiology documented by the clinician.

---

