8.2 Safety outcomes

All AEs (serious and nonserious) will be adjudicated by the Medical Monitor for the following:

- AE term
- Relatedness (to study device and procedure)

The relatedness will be initially determined by the investigator; however, if there is a discrepancy between the investigator and the Medical Monitor, the final analysis will be based on the adjudication determination. Adjudication findings will be entered into the Medrio EDC.

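### SAP 8.2.1 and 8.2.2 define SADE and ADE to include events related only to the procedure, so the reported device-effect counts can exceed those under Protocol 8.4.2

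*SAP*

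**What the plan says.** Protocol 8.4.2 defines an adverse device effect as "Any adverse event related to the use of the study device". Protocol 8.4 lists the event types to be collected, with device-related ADEs and cryotherapy procedure-related AEs as separate entries. The protocol has no separate definition of a SADE; its abbreviation list expands the term, so it reads as an ADE that is also serious.

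The SAP uses wider definitions. Section 8.2.2: "ADEs are AEs that are adjudicated to be related (possibly, probably, or definitely) to the ClariFix device and/or procedure". Section 8.2.1: "SADEs are SAEs that are adjudicated to be related (possibly, probably, or definitely) to the ClariFix device and/or procedure". It plans a total of ADEs and a by-participant listing of SAEs, SADEs and ADEs.

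The two kinds of relatedness are recorded separately. Protocol 8.4.5.2 requires that "All adverse events (AEs) must have their relationship to both the study device and study procedure assessed", and SAP 8.2 has the Medical Monitor adjudicate both.

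Protocol section 3 and SAP 3.1.1 state the primary endpoint as procedure-related SAEs and/or SADEs, and the first secondary endpoint as procedure-related AEs together with ADEs. SAP 8.2.1 and 8.2.2 restate these as participants with any SAE and/or SADE, and any AE and/or ADE.

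**The concern.** Protocol 2.5.1 describes a procedure that includes endoscopy and local anaesthesia, each with its own list of risks. An event caused by either, with no relation to the cryoprobe, is a procedure-related AE under the protocol and an ADE under the SAP. A reader of the report will take *adverse device effect* in the protocol's sense and attribute the event to the device.

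The primary objective is the safety of treatment at the inferior meatus, so what the device did, as distinct from the anaesthetic or the endoscope, is of direct interest. Protocol 9.4.4 also asks for incidence by the event types of Section 8.4, which keep the two apart. The SAP plans no tabulation that does so.

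**Working it through.** The plan gives no figure to reproduce: there is no assumed event rate and no power calculation. The check compares the definitions and then applies them to event counts that the protocol reports.

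**1. The definitions side by side**

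| Event adjudicated as related to | Protocol 8.4 and 8.4.2 | SAP 8.2.1 and 8.2.2 |
|---|---|---|
| Device only | ADE | ADE |
| Device and procedure | ADE | ADE |
| Procedure only | Procedure-related AE | ADE |
| Neither | AE | AE |

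Only the third row differs. Hence ADE count (SAP) = ADE count (protocol) + procedure-only events. The same holds for SADEs among serious events. The difference is never negative.

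**2. Illustration**

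Inputs are the 90-day events of the earlier 100-subject study (Protocol 2.3):
- a = 1 AE that was a probable device effect and procedure-related
- b = 2 procedure-related AEs
- c = 1 SAE possibly related to the device
- d = 1 unrelated SAE

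Assumptions: the two events in b were not device-related; a and b are non-serious and distinct from c and d; the middle causality grade counts as related.

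| Count of events | Protocol definition | SAP definition |
|---|---|---|
| Non-serious ADEs | a = 1 | a + b = 3 |
| All ADEs | a + c = 2 | a + b + c = 4 |
| SADEs | c = 1 | c = 1 |
| Non-serious procedure-related AEs or ADEs (union) | a + b = 3 | a + b = 3 |

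The union in the last row is the form of the first secondary endpoint, and it does not move.

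**3. Chance that the difference arises here**

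If a proportion p of participants has a procedure-only event, the chance of at least one among 30 is 1 − (1 − p)^30. The values of p are assumptions; 2% matches the earlier study if its two events fell in two different subjects.
- p = 1%: 1 − 0.99^30 = 26%
- p = 2%: 1 − 0.98^30 = 45%
- p = 5%: 1 − 0.95^30 = 79%

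**4. The dropped qualifier**

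On the same study's SAEs, SAP 8.2.1 read literally counts c + d = 2, while the endpoint in Protocol section 3 and SAP 3.1.1 counts c = 1. Under the literal text SADEs are a subset of SAEs, and ADEs of AEs, so adding *and/or SADE* or *and/or ADE* changes nothing.

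**5. Causality grades**

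Protocol 8.4.5.2 has five grades: definitely, probably, potentially, unlikely, not related. SAP 8.2.1, SAP 8.2.2 and Protocol 9.4.4 all count possibly, probably and definitely. The grade "Potentially Related" is the only one between probably and unlikely, so it is the evident counterpart of *possibly*.

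**The case against.** The strongest defence is that pooling is open and has a precedent. SAP 8.2.2 is titled as covering both device-related and procedure-related events, and Protocol 9.4.4 itself summarises events related to either. The SAP's SADE and ADE sets coincide with the union endpoints of Protocol section 3. Relatedness to device and to procedure is adjudicated for every event, so the split can be recovered. In a 30-subject feasibility study without power calculations, the matter may never arise: at an assumed 2% rate there is about a 55% chance (100% − 45%) that no participant has a procedure-only event.

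Most of this stands, and it limits the point. It does not justify giving the pooled category a name that the protocol defines more narrowly, or omitting the breakdown by type that Protocol 9.4.4 calls for.

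Three stronger readings are tempting, and the documents do not support them:
- **The primary endpoint is corrupted by the ADE definition.** It is a union, and moving a procedure-only event from one component to the other leaves it unchanged.
- **Events in the middle causality grade will be lost.** That needs a literal match of words, for which the documents show no intent. The mismatch already exists within the protocol (8.4.5.2 against 9.4.4), and SAP 8.2.1 as written counts any SAE whatever its grade.
- **Device effects are overcounted threefold.** The 3-to-1 ratio leaves out the possibly device-related SAE. With it the ratio is 4 to 2, and the SADE count does not differ at all.

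**Conclusion.** The SAP's definitions of ADE and SADE are wider than the protocol's and should be corrected. The error runs in one direction: reported or listed device effects can be too high, never too low, and only if an event related to the procedure alone occurs. The illustrative size is 3 non-serious ADEs instead of 1, or 4 ADEs instead of 2 with the SAE. It rests on another study's event counts and on the assumptions stated with them.

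The union endpoints are unaffected by the relabelling. The missing procedure-related qualifier in SAP 8.2.1 and 8.2.2 is a separate fault in the same sentences, and it can change the primary count (2 instead of 1 in the illustration). The causality wording is a minor harmonisation with no shown effect on any count.

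**What to change.** - In SAP 8.2.1 and 8.2.2, define SADE and ADE as serious and all AEs, respectively, that are adjudicated as related to the ClariFix device, in line with Protocol 8.4.2.
- Tabulate separately the participants and events that are device-related, procedure-related, and either.
- State the primary and first secondary safety endpoints as the union of procedure-related SAEs and SADEs, and of procedure-related AEs and ADEs, as in Protocol section 3 and SAP 3.1.1. This restores the dropped qualifier.
- Use one term for the middle causality grade in Protocol 8.4.5.2, Protocol 9.4.4 and SAP 8.2.1 and 8.2.2, and state that it counts as related.

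The cost is SAP wording, one word in Protocol 9.4.4 or 8.4.5.2, and one extra split in the safety tables. Both relatedness fields are already collected and adjudicated, so trial conduct does not change. The new definition can only lower the ADE and SADE counts or leave them as they are.
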